### **12.3.4 Statistical Analysis of Pharmacokinetic Data**

Individual PTH concentrations (raw and baseline-adjusted) will be listed and summarized with descriptive statistics (number, arithmetic mean, SD, coefficient of variation [CV%], median, minimum, and maximum) by treatment and day. Pharmacokinetic parameters of PTH (based on raw and baseline-adjusted PTH concentrations) will be listed and summarized with descriptive statistics (number, arithmetic mean, SD, coefficient of variation [CV%], median, minimum, maximum, geometric mean, and geometric CV%) by treatment.  $CL/F$  and  $V_{ss}/F$  will be listed, but not included in summary tables.

For Treatment B (repeated in Cohort 1 and Cohort 2) and Treatment E (repeated in Cohort 3 and Cohort 4), summary statistics (for both concentration data and pharmacokinetic parameters) will be prepared by cohort as well as for overall (combining different cohorts).

Figures of individual (overlaid by treatment) and mean (+/-SD) concentration-time profiles (overlaid by treatment as well as by rhPTH(1-84) dosing regimen) of raw and baseline-adjusted plasma PTH will be generated on linear and semi-log scales.

## **12.4 Pharmacodynamic Methods**

All summaries and analyses of the pharmacodynamic data will be based on the Pharmacodynamic Set. After database lock, a visual inspection of concentration-time profiles and pharmacodynamic parameters will be performed by PRA to determine dataset integrity and potential outliers. Descriptive statistics of pharmacodynamic parameters may be calculated with and without subjects with potential outlier data. Subjects with potential outlier data will be reviewed by Shire for inclusion/exclusion from the descriptive statistics on a case-by-case basis. A listing of excluded subjects from the pharmacodynamic analysis will be provided.

### **12.4.1 Raw Pharmacodynamic Data**

Serial blood and urine samples for pharmacodynamic analysis will be collected on Day -1, pre-dose and on Day 1 and Day 2 following the administration of rhPTH(1-84) for the determination of concentrations of serum calcium (uncorrected [total] and corrected for serum albumin levels), phosphate, magnesium, creatinine, albumin,  $1,25(OH)_2D_3$ , and fibroblast growth factor 23 (FGF23), and urinary excretion of calcium, sodium, citrate, phosphate, cAMP, magnesium, and creatinine.

The serum calcium-phosphate product will also be determined. This is calculated as serum calcium concentration (albumin corrected) x serum phosphate concentration.

For pharmacodynamic analyses, concentration values of serum total calcium and albumin-corrected serum calcium, phosphate, magnesium, albumin, creatinine, 1,25(OH)2D3 and FGF23, reported as BLQ will be set to half the LLOQ.

#### **12.4.2 Baseline-adjusted serum Pharmacodynamic Data**

Individual serum concentrations of pharmacodynamic markers, calcium (uncorrected and corrected for albumin), phosphate, magnesium, 1,25(OH)2D3, FGF23, and calcium-phosphate product will be baseline-adjusted at each time point. There will be two baseline definitions, one for Day -1 and one for Day 1. For Day -1, the baseline value is defined as the last non-missing value collected before the start of the active vitamin D administration on Day -1; for Day 1, the baseline value is defined as the last non-missing value collected before the administration of rhPTH(1-84) on Day 1 for each treatment period. Baseline-adjusted concentrations of pharmacodynamic markers are to be calculated by subtracting the appropriate baseline values from the raw concentrations at each time point.

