On Day 1 of Treatment Period 2, subjects will receive the alternative treatment (according to the randomization schedule), following a washout period ( $\geq 5$  days [ie, 120 hours] and  $\leq 30$  days) between administration of the dose or first dose ([for once-daily or twice-daily dosing, respectively] of each treatment period). All investigational product will be administered via SC injection into alternating thighs at each administration.

At each treatment period, subjects will report to the CRC on Day-2, remain in the CRC through Day 2, and be discharged following the last scheduled assessment on Day 2 (investigators may elect, at their discretion, to keep the subject in-clinic after Treatment Period 1 for the duration of the washout period, eg, if the washout period is short [eg, 120-172 hours] or there are any safety concerns).

For once-daily treatments (Treatments B and E), subjects will receive a single subcutaneous dose of rhPTH(1-84) in the morning on Day 1. For twice-daily treatments (Treatments A, C, D, and F), subjects will receive a subcutaneous dose of rhPTH(1-84) in the morning followed by the second dose 12 hours later on Day 1 (in the opposite thigh). If randomized to rhPTH(1-84) with calcium, subjects will take their usual supplemental oral calcium on Day 1 per their usual schedule. Prior to discharge from the CRC at each treatment period, subjects will be given specific instructions for when to take their supplemental oral calcium and active vitamin D supplements during the day(s) when subjects are not in the CRC.

Subjects enrolled in the study must require daily doses of calcium supplements of  $\geq 1000$  mg prior to baseline (Day 1). Subjects enrolled in the study must also require minimum daily doses of active vitamin D of  $\geq 0.25\mu\text{g}$  (ie,  $0.25\mu\text{g}$  calcitriol or equivalent). Subjects will be expected to adhere to standard meals provided during their confinement in the CRC during each period (from check-in on Day -2 until discharge on Day 2). All subjects (in all treatments) will take their usual doses at the usual regimen of supplemental oral calcium and active vitamin D on Day -2 and Day -1. For all subjects in all cohorts, active vitamin D supplements must be withheld on Day 1 through completion of all study procedures on Day 2. Subjects may resume active vitamin D following final procedures on Day 2 at the discretion or direction of the investigator.

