21.	
These changes (item 19 and 20 above) necessitated the reorganization of Table 3 (from the original protocol v 1.0) to be split into 2 separate tables in the amended protocol: Table 3 now summarizes assessments for the QD treatment period, and Table 4 (now added) summarizes assessments for BID treatment period. Subsequent tables in this protocol were renumbered accordingly (ie, Table 4 becomes Table 5, Table 5 becomes Table 6).
 
Reason for change: Clarification to tables.
	Table 3; Table 4 (newly added)

Protocol Amendments		
Summary of Change(s) Since Last Version of Approved Protocol		
Amendment Number	Amendment Date	Global
1	26 Feb 2016	
Item #	Description of Change	Section(s) Affected by Change
22.	
Table 2: Day -1 (Prior to Treatments 1 and 2): Table revised to remove reference relative to BID post evening dose collection time points in the header; streamlined to remove time point/columns where no PD sampling is required.
 
Reason for change: Clarification to table.
	Table 2
23.	
Table 2: Day -1 (Prior to Treatments 1 and 2): PD blood collections were removed at 18, 20, and 22 hours post-dose time points.
 
Reason for change: To correspond to the revised pharmacodynamic sampling time points on Day 1 for QD and BID treatment schedules, and to serve as a baseline (Day -1) comparison for each respective time point on Day 1 of each treatment period. This should enable the assessment and comparisons of the treatment effects on serum calcium and urinary calcium profiles for each of the 6 treatments to their corresponding respective baseline time points.
	Table 2

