On Day 1 of Treatment Period 2, subjects will receive the alternative treatment (according to the randomization schedule), following a washout period (≥5 days [ie, 120 hours] and ≤30 days) between administration of the dose or first dose ([for once-daily or twice-daily dosing,

respectively] of each treatment period). All investigational products will be administered via SC injection into alternating thighs at each administration.

At each treatment period, subjects will report to the CRC on Day-2, remain in the CRC through Day 2, and be discharged following the last scheduled assessment on Day 2 (investigators may elect, at their discretion, to keep the subject in-clinic after Treatment Period 1 for the duration of the washout period, eg, if the washout period is short [eg, 120-172 hours] or there are any safety concerns).

For once-daily treatments (Treatments B and E), subjects will receive a single subcutaneous dose of rhPTH(1-84) in the morning on Day 1. For twice-daily treatments (Treatments A, C, D, and F), subjects will receive a subcutaneous dose of rhPTH(1-84) in the morning followed by the second dose 12 hours later on Day 1 (in the opposite thigh). If randomized to rhPTH(1-84) with calcium, subjects will take their supplemental oral calcium within 30 minutes prior to first dose administration. Prior to discharge from the CRC at each treatment period, subjects will be given specific instructions for when to resume taking their supplemental oral calcium and active vitamin D supplements during the day(s) when subjects are not in the CRC.

Subjects enrolled in the study must require daily doses of calcium supplements of  $\geq 1000$  mg prior to baseline (Day 1). Subjects enrolled in the study must also require minimum daily doses of active vitamin D of  $\geq 0.25\mu\text{g}$  (ie,  $0.25\mu\text{g}$  calcitriol or equivalent). Subjects will be expected to adhere to standard meals provided during their confinement in the CRC during each period (from check-in on Day -2 until discharge on Day 2). All subjects (in all treatments) will take their usual doses of supplemental oral calcium and active vitamin D on Day -2 and Day -1.

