**Table 2: Detailed Schedule of Assessments: Day -1 (Prior to Treatment Periods 1 and 2)**

Study Day	-1																		1
Time point (relative to scheduled dosing time on Day 1 [QD, 1st dose BID]) (hour)	Pre-dose	1	1.5	2	3	4	6	8	10	12	13	13.5	14	15	16	18	20	22	24
Vital signs (blood pressure, pulse) a, b	X c	X		X		X	X	X	X	X	X		X		X	X	X	X	X d
ECG (12-lead) a, e	X c	X		X		X	X	X	X	X	X		X		X	X	X	X	X d
IP administration																			X d
PK blood sampling																			X d
PD blood sampling f	X c		X			X	X	X	X	X		X			X				X d
PD urine sampling g, h	X i	→	→	→	→	→	→	→	→	→	→	→	→	→	→	→	→	→	X d

a An attempt to perform these assessments and procedures should be made for any subject who withdraws or is removed from the study.

b Vital signs should be collected in the supine position at each time point. Subject should also be supine at least 5 minutes prior to vitals collection. Vital signs include blood pressure and pulse.

c These assessments should be performed within 30 minutes prior to the relative time of scheduled administration of IP on Day 1.

d Refer to Detailed Schedule of Assessments (Table 3 and Table 4) for collection time points (note: this time point is the same as the pre-dose collection time point on Day 1).

e ECGs will be performed in triplicate measurement at each time point.

f PD blood sampling assessments will include: total serum calcium, magnesium, phosphate, albumin, creatinine, 1,25-dihydroxyvitamin D, and FGF23.

g 24- hour urine collection for PD analysis will be collected according to the following collection intervals (relative to the Day 1 morning dose): pre-dose, 0-3 hours, 3-6 hours, 6-9 hours, 9-12 hours, 12-15 hours, 15-18 hours, 18-24 hours. ‘X’ denotes the start and stop of the entire urine collection period and ‘→’ denotes continuous collection.

h PD urine collection assessments will include: calcium, sodium, citrate, phosphate, magnesium, cAMP and creatinine.

i The predose timepoint for PD urine sampling is used to signify the action that the subject needs to empty his/her bladder immediately before the start of the 0-3 urine collection based on the predicted dosing time of Day 1. It is not a separate pre-dose urine collection.

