### 12.2 Handling BLQ and Missing Values

The following procedures will be used for raw plasma PTH concentrations, raw serum pharmacodynamic data, and raw urine pharmacodynamic data below the lower limit of quantification (LLOQ):

- Plasma samples that are BLQ are reported as <LLOQ on the data listings, where LLOQ is replaced by the actual value for LLOQ.
- Missing values may be imputed on a case-by-case basis

For plasma PTH concentrations the following guidance will be followed:

- Samples that are BLQ are treated as zero in the calculation of summary statistics (e.g. mean, SD, etc.) for the plasma concentrations at individual time points.
- Mean concentrations are reported as zero if all values are BLQ, and no descriptive statistics are reported. If the calculated mean ( $\pm$  SD) concentration is less than the LLOQ, the value will be reported as calculated. The mean values derived using these conventions will be used to create the mean plasma concentration versus time plots.
- For calculation of area under the plasma concentration curve (AUC), BLQ values are set equal to zero in the dataset loaded into WinNonlin for pharmacokinetic analysis. WinNonlin uses the zero values that occur before the first time point with a concentration greater than LLOQ. Values that are BQL after the first measurable concentration are set to “missing” in the dataset loaded into WinNonlin

For serum PD concentrations the following guidance will be followed:

- Samples that are BLQ are treated as half the LLOQ in non-compartmental PD analysis and the calculation of summary statistics (e.g. mean, SD, etc.) for the plasma concentrations at individual time points.

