#### **12.4.3 Serum Pharmacodynamic Parameters**

Pharmacodynamic parameters will be computed from the individual raw concentrations of serum calcium (mmol/L) (uncorrected and corrected for serum albumin levels), phosphate (mmol/L), magnesium (mmol/L), 1,25(OH)2D3 (pmol/L) and FGF23 using a non-compartmental approach and actual times. pharmacodynamic parameters will be estimated for both Day -1 and Day 1 in each treatment period. Serum calcium will be corrected for serum albumin levels using the following equation:

Corrected calcium (mmol/L) = serum calcium (mmol/L) + 0.02 (40 - serum albumin (g/L))  
(Parent X1, 2009)

The following parameters will be calculated from the raw serum concentration data using WinNonlin Phoenix version 6.3 or higher (Pharsight Corporation, Mountain View, California, USA):

- AUC0-24h: the area under the concentration versus time curve, from time 0 to 24 hours
- TEmax: time to maximum effect
- Emax: maximum effect
- TEmin: time to minimum effect
- Emin: minimum effect

The same parameters will also be calculated for the calcium-phosphate product.

In addition, serum pharmacodynamic parameters will be estimated based on baseline-adjusted serum concentration of pharmacodynamic markers as follows:

- AUCabove: Area under the concentration-time curve that is above the baseline, from time 0 to 24 hours, as calculated by the linear trapezoidal method
- AUCbelow: Area under the concentration-time curve that is below the baseline, from time 0 to 24 hours, as calculated by the linear trapezoidal method
- AUCnet: AUCabove - AUCbelow
- TEmax: time to maximum effect
- Emax: maximum effect
- TEmin: time to minimum effect
- Emin: minimum effect

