#### 12.4.5 Statistical Analysis of Pharmacodynamic Data

For serum pharmacodynamic evaluations, concentrations (raw and baseline-adjusted) of serum total calcium and albumin-corrected calcium, phosphate, creatinine, magnesium, 1,25(OH)2D3 and FGF23 will be summarized with descriptive statistics (number, arithmetic mean, SD, CV%, median, minimum, and maximum) by treatment and day. Pharmacodynamic parameters of serum total calcium and albumin-corrected calcium, phosphate, magnesium, 1,25(OH)2D3 and FGF23 will be summarized with descriptive statistics (number, arithmetic mean, SD, CV%, median, minimum, maximum, geometric mean, and geometric CV%) by treatment and day. This will be done for both raw and baseline-adjusted values, and will be done for both Day -1 and Day 1/2. Note for the Day -1 summaries, the treatment assigned will be the treatment the subject takes the following day.

Individual and mean concentration (raw and baseline-adjusted)-time plots of serum pharmacodynamic markers (serum total calcium and albumin-corrected calcium, phosphate, creatinine, magnesium, 1,25(OH)2D3 and FGF23) will be generated on both linear and semilog scales. These figures will be generated as overlay plots by treatment.

For urine pharmacodynamic evaluations, the individual urinary excretion of calcium, sodium, citrate, magnesium, cAMP, and phosphate and amount relative to creatinine of calcium, sodium, citrate, magnesium, cAMP and phosphate in each collection period as well as over 24 hours will be listed and summarized with descriptive statistics by treatment and day (Day -1 and Day 1/2).

In addition, the renal clearance of calcium, magnesium,, creatinine and phosphate and fractional excretion of calcium, magnesium and phosphate in each collection period will be summarized with descriptive statistics by treatment and day.

Individual and mean urine pharmacodynamic parameters over time (urine collection interval) will be plotted on a linear scale, overlaid by treatment (both Day -1 and Days 1 and 2 will be presented on the same plot).

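### The Day -1 serum PD baseline is tied to each subject's own vitamin D time rather than to the sampling clock, so the reference sample can vary, postdate points it adjusts, or be absent (minor)

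*SAP*

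**What the plan says.** SAP Section 12.4.2 gives two baselines for serum markers. On Day 1 it is the last value before rhPTH(1-84). On Day -1, "the baseline value is defined as the last non-missing value collected before the start of the active vitamin D administration on Day -1". The chosen value is subtracted from the raw concentration at every time point of that day.

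Vitamin D intake on Day -1 is left to the subject's habit. Under Protocol Section 3.1 all subjects "will take their usual doses at the usual regimen of supplemental oral calcium and active vitamin D on Day -2 and Day -1"; SAP Section 2.1 says they "will take their usual doses of supplemental oral calcium and active vitamin D on Day -2 and Day -1". No clock time appears in either.

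The Day -1 samples follow a different clock. The detailed Day -1 schedule (SAP Section 2.4) times them from the scheduled Day 1 dose, and footnote c says of the first draw: "These assessments should be performed within 30 minutes prior to the relative time of scheduled administration of IP on Day 1".

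SAP Section 12.4.3 computes adjusted parameters for Day -1 as well as Day 1, including AUCabove: "Area under the concentration-time curve that is above the baseline, from time 0 to 24 hours, as calculated by the linear trapezoidal method". SAP Section 12.4.5 commits to the summaries: "This will be done for both raw and baseline-adjusted values, and will be done for both Day -1 and Day 1/2". For absent data, SAP Section 12.2 offers only this: "Missing values may be imputed on a case-by-case basis".

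**The concern.** Nothing links the two clocks. The rule can be programmed, because Protocol Section 5.2 requires vitamin D times to be recorded for Day -1. What it returns, however, depends on when each subject happens to take the tablet. The Day -1 adjusted summaries could therefore pool subjects whose curves are measured from different hours of the day, subtract a later sample from earlier ones, or have no reference for some subjects and no stated rule for that case. Protocol Section 9.4 says the SAP will describe how missing data are addressed; a case-by-case provision does not settle this.

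At stake is whether the Day -1 adjusted tables mean the same thing for every subject and sit sensibly beside the Day 1 tables. The protocol's amendment history, cited here only for purpose, explains that the Day -1 draws were matched to the Day 1 times "to serve as a baseline (Day -1) comparison for each respective time point on Day 1 of each treatment period".

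**Working it through.** **Inputs.** In the detailed Day -1 schedule, PD blood is drawn at 0 (predose), 1.5, 4, 6, 8, 10, 12, 13.5 and 16 h, with the 24-h point being the Day 1 predose sample. That is 9 draws per period and 9 × 2 = 18 over two periods, which reproduces the 18 baseline PD samples in Protocol Table 6.

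**Time 0.** SAP Section 12.4.3 does not define time 0 for Day -1 and specifies actual times. That the 0-24 h window starts at the planned dosing clock time is inferred from the schedule heading.

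**Rule.** Reference = last sample drawn before the first active vitamin D intake on Day -1. Earlier points adjusted = number of samples before that reference. Share of the window before the reference = reference hour / 24.

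**Applied to an assumed 08:00 dose, nominal draw times, assumed intake times:**

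| Vitamin D intake | Hours from clock | Reference | Earlier points adjusted by it | Share of 24 h before it |
|---|---|---|---|---|
| 07:00 | -1 | none on Day -1 | not applicable | not applicable |
| 08:30 | 0.5 | 0 h | 0 | 0% |
| 13:00 | 5 | 4 h | 2 | 4/24 = 17% |
| 22:00 | 14 | 13.5 h | 7 | 13.5/24 = 56% |

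Any intake after the time-0 draw and before the 1.5-h draw gives the 0-h sample, which is presumably what was intended. The 22:00 row is the extreme case and would need a first intake that late.

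**Sensitivity to the draw window.** With a 09:00 dose, a 13:00 intake coincides with the nominal 4-h draw. If the sample is taken first, the reference is the 4-h sample (17% of the window before it); otherwise it is the 1.5-h sample (1.5/24 = 6%). Protocol Section 7.3.4 allows ±15 minutes from 4 h onward. If that applies on Day -1, the boundaries between reference samples are not exact.

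**No reference on Day -1 (07:00 row).** In Period 1 the biochemistry panel (Protocol Section 7.3.2.5), drawn at screening and Day -2, includes calcium, phosphorus, magnesium and albumin but not 1,25(OH)2D3 or FGF23. Those two markers have no earlier scheduled value. For the others, Section 12.4.2 does not say whether safety chemistry may serve as a PD baseline.

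**Effect of a shifted reference.** If the reference is higher by d, every adjusted value falls by d. AUCnet over 0-24 h therefore changes by -24 × d, and Emax and Emin each change by -d. For assumed serum calcium shifts of 0.02, 0.05 and 0.10 mmol/L, AUCnet changes by -0.48, -1.2 and -2.4 mmol·h/L. The documents supply no value for d; this shows only how the error carries through.

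**Reach.** Adjusted concentration Tables 2.2.9-2.2.15 (7) plus adjusted parameter Tables 2.3.2.1-2.3.2.7 (7) = 14, Day -1 part only, with the matching 2.5.x and 2.7.x figures.

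**The case against.** The strongest defence is that the rule is deliberate. The two definitions are parallel: each takes the last value before that day's agent, vitamin D on Day -1 and rhPTH(1-84) on Day 1. Calcitriol is 1,25(OH)2D3, one of the adjusted markers, so a time-0 sample drawn after a calcitriol dose may already contain that dose. This stands as a real cost of changing the rule. It does not justify subtracting a later sample from earlier points. Nor is the pre-intake value free of vitamin D, since subjects also take it on Day -2.

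It is also fair to say that the consequences are limited and conditional. The study is descriptive, no formal Day 1 versus Day -1 contrast is planned, and the raw Day -1 and Day 1 profiles are both tabulated and allow the time-matched comparison. Nothing shows that any subject takes vitamin D at 13:00 or 22:00. All of this stands and sets the severity.

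A reader might go further in three ways that the documents do not support:

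- **Material distortion of the calcium results.** One could set the assumed d values against the maximum mean rise of about 0.125-0.175 mmol/L in Protocol Section 2.1. No d is given or derivable, and the Day 1 adjusted results do not use this baseline.
- **Contamination of Period 2 by Period 1 post-dose samples.** Read literally, the Day -1 rule has no look-back limit. But the sentence ends by referring to each treatment period, which can be taken to confine both definitions to their own period.
- **Day -2 chemistry would be carried in.** This is only one reading. SAP Section 12.4.1 describes PD data as Day -1, predose, Day 1 and Day 2 samples, so the value might simply be left missing.

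**Conclusion.** The point holds as a minor defect in an analysis definition. The stated rule can return the 0-h sample, a later sample that is then subtracted from earlier points, or no Day -1 sample, depending on an intake time that the plan does not fix. How often this happens and how much it moves any summary cannot be estimated from the documents. If every subject takes vitamin D between the first draw and 1.5 h, nothing changes.

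Only the Day -1 part of the 14 tables and their figures is affected. Raw profiles, Day 1 adjusted values, urine parameters and PK are not. The conclusion rests on the texts placed side by side, on assumed intake times and dosing clock for the examples, and on the inference that Day -1 time 0 is the planned dosing clock time. It takes no view on when vitamin D should be given.

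**What to change.** In SAP Section 12.4.2:

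- define the Day -1 baseline for every serum marker as the scheduled Day -1 time-0 sample of the same period, drawn within 30 minutes before the planned dosing clock time;
- state that time 0 for Day -1 is that clock time;
- if that sample is missing, set the subject's Day -1 adjusted values for that period to missing, with no carry-over and no case-by-case imputation of this baseline.

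In the medications-of-interest listing already planned in SAP Section 9, flag subjects whose Day -1 vitamin D came before the time-0 draw.

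The drafting cost is a few sentences and one flag; the sample is already collected and the intake times already recorded. There are two analytic costs. For flagged subjects the baseline is post-vitamin D, which matters most for 1,25(OH)2D3, so that marker's Day -1 adjusted values should be read with the flag. And a subject without a time-0 sample loses Day -1 adjusted values, because Day -1 would no longer share the last-non-missing rule used on Day 1.
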